# 7.7 Adverse Event Monitoring

Safety and tolerability will be monitored by AEs determined every 2 weeks while on treatment. It is expect that about 10% of subjects will have intolerable toxicity, requiring discontinuation of therapy. If the number of subjects discontinuing therapy is greater than 10% (p<0.05), this therapy will be considered intolerable in this population.

Participating sites will enter data every two weeks at a minimum. Participating sites will also notify the coordinating center of Grade 3 and higher adverse events and serious adverse events within 24 hours of occurrence or notification. The study chair (PI) will be notified of such events by the coordinating center team at Washington University, the Lead Protocol Organization (LPO) and Duke University, the Lead Academic Organization (LAO). The coordinating center team and LAO and LPO investigators will have a weekly conference call to review subject enrollment, study progress, and available safety data including those generated from the study database. In addition, there will be monthly conference calls with the coordinating center, study chair, and participating sites (study nurses/ coordinators/ investigators) to review study progress and safety data.

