#### 13.2 Study Design

At least 20 evaluable patients will be enrolled for this study. Evaluable patients will be those patients who received study medication. The sample size of 20 patients is based on Simon's Optimal 2-stage design, with the assumption that an overall response rate of 40% is the minimum response rate that would be considered for further analysis of this approach, compared to a rate of 10% under null hypothesis. Thus, 20 subjects are required to with a one-side type 1 error rate of 5% and a power of 90%. If 1 or fewer responses are seen among the first 9 subjects enrolled, the trial is stopped early for futility. In contrast, if 2 or more responders are observed out of the 9 patients in the first stage, additional 11 patients will be enrolled in the 2nd stage. In a multicenter study such as this, however, it is difficult for a trial to reach the planned sample exactly. The investigators would not turn away patients who have already been approached for participation just because the number of patients needed has been met. Therefore, we adopted a flexible Phase II design (Chen and Ng 1998) to allow the actual number at final stage to deviate slightly from

what is planned. Due to the expected relatively low accrual rate, we expect that the interim analysis could be performed at the designed sample size. Only the decision boundaries at the 2nd-stage are determined following Chen and Ng's flexible design and programed by the study statistician [57]. That is, if 5 or more responders are observed out of 20-23 patients, or 6 or more responders are observed out of 24-25 patients, we would conclude that preliminary evidence for efficacy exists and that further investigation of the treatment is warranted.

The interim analysis will be based upon independent review of response, with a minimum time frame of 2 months for the interim analysis. Accrual will not be halted during the interim analysis.

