#### 13.3 Data Analysis

Data analysis of the study will be descriptive in nature. Demographic and clinical characteristics of the sample, toxicity by grade, as well as tumor response, duration of response, and length of follow-up will be summarized using descriptive statistics. Binomial proportions and their 90% confidence intervals will be used to estimate the response rates of therapy. Binomial proportions and their 90% confidence intervals will also be calculated for the efficacy based on immune response criteria (Appendix D). The Kaplan-Meier method will be used to evaluate the response duration. Analysis of variance methods will be used to evaluate the effects of treatment and time on the viral load measurements, as well as measurements of viral transcripts. The incidence of toxicities will be estimated using the binomial proportion and its 90% confidence interval. A proportional hazards analysis with viral load measures as time dependent covariates will be used to evaluate the effects of treatment and structure the effects of these measures on duration of response. Detailed analysis of correlative studies and biomarkers are listed in Section 9.

The safety and tolerability will be monitored every 2 weeks. All patients who receive treatment with nivolumab will be eligible for safety and tolerability analysis. A Bayesian sequential monitoring method [58] will be used for safety analysis and the stopping rule is defined as  $Pr(\theta>0.10 | data)>0.90$ , where  $\theta$  denotes the proportion of patients who discontinue therapy due to intolerable toxicity. That is, enrollment will be stopped early whenever, given the accumulated observed data, there is >90% probability that the discontinuation of therapy is greater than 10%. Specifically, enrollment will be stopped early if 3 patients discontinue therapy in the first 12 patients, or 4 patients discontinue therapy in the first 19 patients, or 5 patients discontinue therapy before the last patient enrolled. These boundaries were obtained using the free-download software Multc99 (version 2.1) from M.D. Anderson Cancer Center. We assume that the parameter  $\theta$ follows a prior distribution of beta ( $\alpha$ ,  $\beta$ ), with  $\alpha$  and  $\beta$  representing the number of patients discontinuing and continuing therapy respectively.

	Ethnic Categories				T ( )
Racial Categories	Not Hispanic or Latino		Hispanic or Latino		Total
	Female	Male	Female	Male	
American Indian/ Alaska Native	0	0	0	0	0

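### Section 13.3: the toxicity stopping rule, applied with any searched prior that reproduces its printed limits, also stops at 2 discontinuations in the first 2 to 4 patients, but the printed list has no row below 3

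*Combined protocol and SAP*

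**What the plan says.** Section 13.3 (Data Analysis) defines θ as the proportion of patients who discontinue because of intolerable toxicity and sets the rule Pr(θ>0.10 | data)>0.90. In words, "enrollment will be stopped early whenever, given the accumulated observed data, there is >90% probability that the discontinuation of therapy is greater than 10" percent. On timing it says "The safety and tolerability will be monitored every 2 weeks". It sets no minimum number of patients or events before the rule applies.

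The next sentence presents the same rule as counts, the first being "enrollment will be stopped early if 3 patients discontinue therapy in the first 12 patients". Two further limits follow: 4 events among the first 19, and 5 events at any point until the final patient is enrolled. The counts are attributed to a named boundary program. The prior is a beta distribution whose parameters are described only as "representing the number of patients discontinuing and continuing therapy respectively", without values. Section 13.2 plans 20 patients and allows up to 25.

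**The concern.** The list is offered as the rule in numbers, so the two should give the same decision for every possible history. The list begins at 3 events. A posterior-probability rule with no minimum can also be met by 2 events when few patients have been treated. If it is, a monitor holding the list would continue enrollment where the stated rule stops it.

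This affects the first few patients on treatment. Safety and tolerability are part of the primary objective, and section 2.2.5 names a theoretical risk that checkpoint inhibitors promote HTLV-1 inflammatory disorders. Because the prior is not given, a reader cannot tell which early rows follow from it.

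**Working it through.** **Inputs.** From 13.3: threshold rate 0.10, probability cut-off 0.90, limits 3/12, 4/19 and 5. From 13.2: planned N of 20. Assumed, because the plan gives no values: the beta parameters α and β, searched over grids.

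**Formula.** After k discontinuations in n patients, Pr(θ>0.10) = 1 − F(0.10; α+k, β+n−k), where F is the beta distribution function. Stop if this exceeds 0.90.

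**Reproducing the plan's limits.** A prior fits if 3/12 and 4/19 stop and 3/13 and 4/20 do not. Beta(1,6) fits and can be checked by hand, because for whole numbers Pr(Beta(a,b)>0.10) = Pr(Bin(a+b−1, 0.10) ≤ a−1):

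- 3/12: Pr(Bin(18, 0.10) ≤ 3) = 0.902, stop. 3/13: Pr(Bin(19, 0.10) ≤ 3) = 0.885, continue.
- 4/19: Pr(Bin(25, 0.10) ≤ 4) = 0.902, stop. 4/20: Pr(Bin(26, 0.10) ≤ 4) = 0.888, continue.
- 5/25: 0.917, stop.

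The printed rows are therefore reproducible.

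**The same prior at 2 events.** 2/4: Pr(Bin(10, 0.10) ≤ 2) = 0.349 + 0.387 + 0.194 = 0.930, stop. The list continues.

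**Other priors that fit the list.**

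| Prior | 1/1 | 2/4 | 2/5 | 2/6 | 3/12 | 4/19 |
|---|---|---|---|---|---|---|
| Beta(0.01,0.09) | 0.991 | 0.971 | 0.946 | 0.917 | 0.910 | 0.901 |
| Beta(0.5,3) | 0.878 | 0.945 | 0.923 | 0.898 | 0.904 | 0.901 |
| Beta(1,6) | 0.850 | 0.930 | 0.910 | 0.889 | 0.902 | 0.902 |
| Beta(2,12) | 0.842 | 0.917 | 0.902 | 0.885 | 0.902 | 0.906 |

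**Grid search.** The fitting region is bounded (α to about 6, β to about 39), so a search can cover it. Every fitting prior exceeds 0.90 at 2/2, 2/3 and 2/4. The lowest 2/4 value is 0.901, on a fine grid at the strong-prior corner. On an evenly spaced grid (α in steps of 0.05, β in steps of 0.1), about 71% of fitting priors also stop at 2/5 and 24% at 2/6. None stops at 2/7. About 11%, all vague, stop at 1/1. All stop at 5/25.

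**Size, within the first 6 patients.** Outcomes are assumed known at once, with one look per patient.

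- Listed rows: Pr(3 or more in 6). At 10%: 1 − 0.5314 − 0.3543 − 0.0984 = 1.6%. At 30%: 1 − 0.1176 − 0.3025 − 0.3241 = 25.6%.
- With a 2/4 row: Pr(2 or more in 4) + Pr(1 in 4) × Pr(2 in the next 2). At 10%: 0.0523 + 0.2916 × 0.01 = 5.5%. At 30%: 0.3483 + 0.4116 × 0.09 = 38.5%.

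**Size, by 20 patients (exact enumeration).** At 10%: 15.6% as listed, 17.4% with 2/4. At 30%: 88.7% and 89.2%.

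**Delay check.** Suppose each outcome counts only once 2 more patients are enrolled, with everyone enrolled in the denominator. Stopping within the first 6 patients at 30% is then 8.4% as listed and 12.8% with 2/4. With a delay of 3 patients it is 2.7% either way, and by 20 patients 77.6% either way.

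**The case against.** The strongest reply is that the list is the operating boundary: it gives a monitor a clear instruction, and the boundary program may have been run with a minimum or with cohort looks. That may be so, but 13.3 states no minimum and words its rule as applying at any time. The list also shows no minimum by patient number, since 3 events in 3 patients already meets its first row.

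A second reply concerns the fitting condition. With 20 patients planned, the 4-event row might have been cut off, so 4/20 need not be a non-stopping point. If 4/20 may stop, some strong priors escape at 2/4. They start at about α = 7.25 and β = 47.4, which is worth about 55 patients, more than the trial enrolls. With α up to 10 they are about 2% to 4% of fitting priors, and all still stop at 2/2 and 2/3. The share grows if much stronger priors are admitted, but exceptions at 2/3 appear only for priors worth about 300 patients, and none was found at 2/2. The disagreement narrows and does not disappear.

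Third, outcomes may be slow. Some discontinuation criteria in section 5.3 take more than 6 weeks to be met, and no accrual rate is given. This stands: the practical gap shrinks with delay and can vanish. Against it, section 13.2 says "Due to the expected relatively low accrual rate, we expect that the interim analysis could be performed at the designed sample size", so slow enrollment is expected and early looks with few patients are realistic.

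Finally, section 7.7 provides 24-hour notification of Grade 3 and higher events and weekly calls. That is real oversight, but it is not a formal stopping criterion.

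**Conclusion.** The point holds in a narrow form. With 2 discontinuations in the first 2 to 4 patients, the rule in 13.3 stops enrollment and its list does not. This is true for every searched prior that gives 3/12 and 4/19 as exact last stopping points. The effect falls on the earliest patients: 4 points at a true 10% rate and 13 points at 30% within the first 6, with immediate outcomes. By 20 patients it is 1.8 points and 0.5 points. It is worth correcting because a safety decision is undefined, not because the overall operating characteristics are poor.

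Three stronger readings are not supported:

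- A reader might infer that the printed rows are wrong. They reproduce under many ordinary priors.
- A reader might infer that one event in the first patient would usually stop the trial, or that a 2-in-6 row is implied. Only vague priors give the former and a minority of fitting priors the latter. Because the plan states no prior, neither can be attributed to it.
- A reader might infer that 13.3 contradicts the p<0.05 criterion in 7.7. That criterion concerns calling the therapy intolerable, whereas 13.3 concerns stopping enrollment.

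**What to change.** In 13.3, state the α and β that were used and rerun the boundary program with them. Then make rule and list match in one of two ways: print the early row or rows that the prior implies, or state the minimum number of patients or events that was intended. Which applies is for the sponsor to reconcile. A minimum written as a number of patients should be checked against the first printed row, which already stops at 3 events in any number up to 12.

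The cost is one program run and a few words in the plan, with no new data. The downside of a 2-event row is more stopping when the true rate is only 10%. By 20 patients it rises from 15.6% to 17.4% with 2/4 (about 2 points), 18.5% with 2/5, or 20.0% with 2/6 (about 4 points). Mean enrollment, capped at 20, falls from 18.7 to 18.2 with 2/4 or 17.7 with 2/6. Stating a minimum instead avoids this but leaves the earliest patients without a formal stop, and the plan should then say so.

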#### PLANNED ENROLLMENT REPORT

Racial Categories	Ethnic Categories				
	Not Hispanic or I	Latino	Hispanic or La	atino	Total
	Female	Male	Female	Male	
Asian	1	1	0	0	2
Native Hawaiian or Other Pacific Islander	1	1	0	0	2
Black or African American	6	6	0	0	12
White	1	1	1	1	4
More Than One Race	0	0	0	0	0
Total	9	9	1	1	20

PHS 398 / PHS 2590 (Rev. 08/12 Approved Through 8/31/2015)

OMB No. 0925-0001/0002

#### **13.4** Reporting and Exclusions

#### **13.4.1** Evaluation of Toxicity

All patients will be evaluable for toxicity from the time of their first treatment with nivolumab.

#### **13.4.2** Evaluation of Response

All patients included in the study must be assessed for response to treatment, even if there are major protocol treatment deviations or if they are ineligible. Each patient will be assigned one of the following categories: 1) complete response, 2) partial response, 3) stable disease, 4) progressive disease, 5) early death from malignant disease, 6) early death from toxicity, 7) early death because of other cause, or 8) unknown (not assessable, insufficient data). [Note: By arbitrary convention, category 8 usually designates the "unknown" status of any type of data in a clinical database.]

All of the patients who met the eligibility criteria (with the possible exception of those who received no study medication) should be included in the main analysis of the response rate. Patients in response categories 4-9 should be considered to have a treatment failure (disease progression). Thus, an incorrect treatment schedule or drug administration does not result in exclusion from the analysis of the response rate. Precise definitions for categories 4-9 will be protocol specific.

All conclusions should be based on all eligible patients. Subgroup analyses may then be performed on the basis of a subset of patients, excluding those for whom major protocol deviations have been identified (*e.g.*, early death due to other reasons, early discontinuation of treatment, major protocol violations, etc.). However, these subgroup analyses may not serve as the basis for drawing conclusions concerning treatment efficacy, and the reasons for excluding patients from the analysis should be clearly reported. The 95% confidence intervals should also be provided.

#### APPENDIX A PERFORMANCE STATUS CRITERIA

ECOG Performance Status Scale		Karnofsky Performance Scale			
Grade	Descriptions	Percent	Description		
0	Normal activity. Fully active, able to carry on all pre-disease	100	Normal, no complaints, no evidence of disease.		
0	performance without restriction.	90	Able to carry on normal activity; minor signs or symptoms of disease.		
1	Symptoms, but ambulatory. Restricted in physically strenuous activity, but ambulatory and able to	80	Normal activity with effort; some signs or symptoms of disease.		
 carry out work of a light or sedentary nature ( e.g. , light housework, office work).		70	Cares for self, unable to carry on normal activity or to do active work.		
	In bed <50% of the time. Ambulatory and capable of all self-	60	Requires occasional assistance, but is able to care for most of his/her needs.		
2	care, but unable to carry out any work activities. Up and about more than 50% of waking hours.	50	Requires considerable assistance and frequent medical care.		
2	In bed >50% of the time. Capable of only limited self-care, confined	40	Disabled, requires special care and assistance.		
3	to bed or chair more than 50% of waking hours.	30	Severely disabled, hospitalization indicated. Death not imminent.		
4	100%bedridden.Completelydisabled.Cannot carry on any self-	20	Very sick, hospitalization indicated. Death not imminent.		
4	care. Totally confined to bed or chair.	10	Moribund, fatal processes progressing rapidly.		
5	Dead.	0	Dead.		

### APPENDIX B LIST OF PROHIBITED MEDICATIONS

The following medications may not be taken while participating on this study through 6 weeks after the last dose of protocol treatment:

- Any non-study anti-cancer agent (investigational or non-investigational)
- Any other investigational agents
- Any other CTLA-4 inhibitors or agonists
- CD137 agonists, PD-1 inhibitors
- Immunosuppressive agents, unless indicated to manage study therapy induced irAEs
- Chronic systemic corticosteroids, unless indicated to manage study therapy induced irAEs or chronic GVHD at a stable dose prior to study entry
- Any non-oncology vaccine therapies used for the prevention of infectious diseases (for up to 30 days prior to or after any dose of study drug, however it is suggested that routine vaccinations, including seasonal influenza, be given at least 2 weeks prior to study treatment)

#### APPENDIX C IMAGING METHODOLOGIES

Contrast enhanced CT or enhanced MRI are the preferred imaging modalities to be used. Chest x-rays performed during the screening phase (and repeated at anytime during the study if clinically indicated) may be used as supportive data, as an accessory to the CT chest scans.

The same imaging techniques used at screening MUST be used at all subsequent time points to permit accurate, comparable measurement of lesions. All imaging data are to be collected on film or in digital format.

#### CT/MRI of the Chest/Abdomen/Pelvis

CT/MRI imaging of the chest, abdomen and pelvis is required at Screening and at each tumor assessment visit as indicated in Table 1, Table 2, and Table 3, regardless of the location of known metastases. In addition, CT/MRI scans must be obtained of anatomic regions not covered by the chest, abdomen and pelvic scans, in subjects where there is clinical suspicion of deep soft tissue metastases (eg, lesions in the thigh). Such additional CT/MRIs will be required at Screening only when deep soft tissue disease is known/suspected and must be consistently repeated at all subsequent tumor assessment visits.

#### Non-radiographic Assessments/Digital Photography

These should be made at the sites and recorded in the source documents. Visible skin lesions should be measured clinically and documented digitally using standardized photographic images, including a ruler for scale as part of the image.

#### **Image Acquisition Guidelines**

Similar methods of tumor assessment and similar techniques must be used to characterize each identified and reported lesion at Screening and during the Induction and Maintenance Phases. All measurable and non-measurable lesions should be assessed at Screening and at the defined tumor assessment time points (see Table 1, Table 2, and Table 3). Additional assessments may be performed, as clinically indicated, if there is a suspicion of progression or for confirmation of response. The Investigator will base response to treatment on the irRC (see Appendix D). Imaging-based evaluation is preferred to physical examination. Helical (spiral) CT scans of chest, abdomen and pelvis are preferred. If not available, conventional (non-helical, non-spiral CT) should be used.

IV contrast should be used for all CT scans. If i.v. contrast is contraindicated, CT may be performed without contrast. Alternatively, MRI can be used to assess lesions in the subject. Subjects who develop contrast allergy after study enrollment may be followed by MRI for subsequent tumor measurements. Sections should be contiguous, similarly sized and consistent from visit-to-visit. Section thickness must be based on institutional standards (eg, from 5 to 8 mm; 10 mm cuts are not recommended). Chest x-ray, ultrasound, and PET scans are not acceptable methods to measure disease for the purposes of this study.

#### APPENDIX D IMMUNE-RELATED RESPONSE CRITERIA

Immune-related Response Criteria (irRC) are derived from modified World Health Organization (mWHO) conventions. Assessments of lymph nodes are derived from current RECIST guidelines.

#### 1.1.1.1.1 Definitions of Measurable/non-Measurable Lesions

All measurable and non-measurable lesions should be assessed at Screening and at the defined tumor assessment time points (see Table 1). Additional assessments may be performed, as clinically indicated for suspicion of progression. The Investigator will base response to treatment using the irRC.

#### 1.1.1.1.2 Measurable Lesions

Measurable lesions are lesions that can be accurately measured in 2 perpendicular diameters, with at least 1 diameter  $\ge 20$  mm and the other dimension  $\ge 10$  mm (10 mm x 10 mm for spiral CT with cuts of 5 mm). The area will be defined as the product of the largest diameter with its perpendicular.

Lymph nodes may also be considered measurable. To be considered pathologically enlarged and measurable, a lymph node must be at least 15 mm in short axis when assessed by CT scan (CT scan slice thickness recommended to be no greater than 5 mm).

#### 1.1.1.1.3 Non-Measurable Lesions

Non-measurable (evaluable) lesions are all other lesions, including unidimensional measurable disease and small lesions (lesions without at least 1 diameter  $\geq 20$  mm, or pathological lymph nodes with short axis  $\leq 15$  mm), and any of the following: lesions occurring in a previously irradiated area (unless they are documented as new lesions since the completion of radiation therapy), bone lesions, leptomeningeal disease, ascites, pleural or pericardial effusion, lymphangitis cutis/pulmonis, abdominal masses that are not pathologically/cytologically confirmed and followed by imaging techniques and cystic lesions. Lymph nodes that have a short axis < 10 mm are considered non-pathological and should not be recorded or followed.

#### 1.1.1.1.4 Definitions of Index/non-Index Lesions

Measurable lesions, up to a maximum of 5 lesions per organ and ten lesions in total, must be identified as index lesions to be measured at Screening. The index lesions should be representative of all involved organs. In addition, index lesions must be selected based on their size (eg, lesions with the longest diameters), their suitability for accurate repeat assessment by imaging techniques, and how representative they are of the subject's tumor burden. At Screening, a Sum of the Product Diameters (SPD) for all index lesions will be calculated and considered the baseline SPD. The baseline sum will be used as the reference point to determine

<sup>1 Eisenhauer EA, Therasse P, Bogaerts J, Schwartz LH, Sargent D, Ford R, et al. New response evaluation criteria in solid tumors: Revised RECIST guideline (version 1.1). Eur J Can. 2009;45: 228 247.

the objective tumor response of the index lesions at tumor assessment.

